1.0 Background and Rationale

Small procedures are an everyday occurrence in the pediatric emergency department. Medical procedures often elicit anxiety, which amplifies the pain response.ⁱ Laceration repair is one of the most common procedures performed. Simple laceration repair can be challenging not from a technical standpoint, but due to patient cooperation secondary to patient pain and anxiety.ⁱⁱ Usually, uncooperative children squirm, kick, twist, and scream; this is physically challenging during a laceration repair. It is the norm for patients to require distraction, analgesia, and anxiolytics as well as physical holding in order to achieve adequate patient stillness for safe repair. Typical passive distraction methods include watching television, playing on a tablet or phone, parental engagement, or Child Life involvement. Distraction is an accessible, low-cost, and non-pharmacologic intervention.

Virtual reality is an evolving technology that allows a viewer to be immersed into a simulated environment using a head mounted device as well as hand-held controllers. Immersive virtual reality is an active form of distraction. Children who actively perform tasks or engage in activities forget about their pain and fear.ⁱⁱⁱ Virtual reality has been documented in the literature as a safe and effective tool to reduce both pain and anxiety surrounding painful procedures in pediatrics as a distraction technique.^{iv} It has also been theorized to diminish pain signals during painful procedures.^v This technology has been studied in burn scrubs,^{vi} wound dressing changes,^{vii} immunizations,^{viii} venipuncture,^{ix} lumbar punctures,^x and dental procedures^{xi} in pediatrics. However, virtual reality (VR) has not been well described for laceration repair in the pediatric emergency department setting. Side effects might include nausea, vomiting, motion sickness, but these have not been proven to be significant outcomes in the literature.^{xii}

In our emergency department, the standard of care involves topical lidocaine/epinephrine/tetracaine (LET) cream and/or subcutaneous lidocaine, positioning, Child Life staff, and distraction. For some children, oral or intranasal anxiolysis is necessary as well as physical holding. Our aim for this study is to determine if Virtual Reality goggles can improve patient pain and anxiety scores during simple laceration repair when compared to standard passive distraction techniques.

2.0 Objectives

The objective of this study is to determine if VR goggles can decrease patient pain and anxiety during simple laceration repairs. The primary outcome will be pain scores as assessed by the validated Wong Baker Faces Scale and anxiety scores as assessed by the validated Children's Fear Scale. A validated System Usability Scale (SUS) will be measured for each enrolled participant that used the VR goggles. Secondary outcomes include time of procedure, use of physical holding, adverse outcomes, and pharmacologic interventions.

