3.0 Project Procedures

This will be a randomized pragmatic study for all patients ages 6-17 years with simple lacerations. Simple lacerations will be defined as lacerations within the scope of pediatric emergency medicine providers AND not requiring sedation or operative intervention. Subjects will be identified by the Emergency Department staff for enrollment. The goal number of enrolled participants will be 480, including 240 patients randomized into two groups, 120 per group, and 240 parents/guardians. The Emergency Department accepted to participate in this study and ED providers will complete the provider's survey. After signing the consent and assent form when appropriate, the patients will be randomized to either receive the standard of care or standard of care with immersive virtual reality goggles. Consent and assent will be obtained in the patient rooms within the emergency department. The standard of care shall be defined to include any of the following: local analgesia (topical LET and/ or subcutaneous lidocaine), oral or intranasal midazolam, distraction, Child Life Staff, or physical holding. Because each of the aforementioned interventions may vary between patients, it cannot be truly standardized; hence, this will be considered a pragmatic study. Patients randomized to the VR arm will receive the other standard procedures as well with VR goggles as an adjunct. Exclusion criteria include a history of epilepsy, visual or hearing impairment, or intellectual disability that would preclude use of VR goggles as determined by the guardian. Additionally, any lacerations around the eyes, eyebrows, and nose will be excluded as well as patients requiring sedation. Non-English speaking patients will be excluded as well. Hand lacerations will not be excluded.

Participants will be identified by ED staff following evaluation of the laceration. The ED staff will be given a flowchart with eligibility criteria. All interested participants who meet eligibility criteria will be consented. A research team member will obtain consent from parents or guardians by providing and reviewing the consent form (see Subject Consent Form). For patients who are between 8 and 17 years of age, a research team member will obtain assent by providing and reviewing the assent form (see Subject Assent Form). Consent and assent will be obtained in the patient's ED room.

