Patients will be separated into groups age 6-11 and 12-17. Patients will be randomized via a selection of a sealed envelope which will contain instructions for use of the VR goggles. The goggles utilized will be Lenovo Mirage Solo with DayDream, which are standalone VR headset with WorldSense Body Tracking. Research staff will coach the child on age-appropriate games, as previously determined by Lenovo.

The goggles will be cleansed with Oxivir Tb disinfectant wipes after each use and allowed to dry in room air prior to next use. Education will be provided to all ED providers on the proper cleansing protocol for the VR goggles (Figure 4). The disinfectant protocol will be available for all users during the study, and has been approved by the director of Infection Control at Children's Hospital of the King's Daughters.

Following the laceration repair, the patient, guardian and health care provider will be surveyed (Figure 1, 2, and 3) on paper surveys. The survey includes Likert-type scale questions, binary

questions as well as incorporates the Wong Baker Faces Pain Scale and Children's Fear Scale. The duration of the procedure will be recorded by the healthcare provider who completed the laceration repair. Time of procedure will be defined as from the time of irrigation to wound dressing. Patients and parents will both be filling out their own individual surveys. The parent should complete the survey first before the child should the child need assistance with completion. Patients and parents may decline to participate in any survey at any time.

The recruitment period will be from November 2021 until February 2021. Enrolled participants will not be compensated, and enrollment will be completely voluntary.

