4.0 Statistical Analysis

Continuous variables will be presented as mean, standard deviation, median, 25th, and 75th percentile. Categorical variables will be presented as frequency and percentage. Generalized Linear Model (GLM) will be used to assess the effect of intervention on the outcomes of the surveys. The correlation between provider's, parent's, patient's survey will be analyzed using the Spearman's correlation test. All statistical tests will be performed using the R software. All statistical tests will be 2-sided and $p < 0.05$ will be considered as statistically significant.

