6.0 Budget

The Virtual Reality goggles are property of the Children's Hospital of the King's Daughters Child Life department. They will be stored in a locked drawer within the CHKD Emergency Department. This project is unfunded.

Figure 1. Use of Immersive Virtual Reality for Laceration Repairs in the Pediatric Emergency
Department
Patient Survey

1. How old are you? _____

2. Have you had stitches before? Yes
 No
 Unsure

3. Have you ever used Virtual Reality (VR) goggles before today? Yes
 No
 Unsure

4. Did you use VR goggles for your stitches today? Yes
 No

5. Would you use VR goggles again to get stitches? Yes
 No

6. During your stitches, did you have any of the following (select all that apply)?
 I did not experience any symptoms
 Dizziness
 Headache
 Nausea
 Vomiting
 Other (describe below)

7. How do you think the stitches went overall? Not well at all
 Somewhat not well
 Neutral
 Somewhat well
 Very well

8. The virtual reality goggles made the stitches seem less scary.
 Strongly disagree
 Disagree
 Neutral
 Agree
 Strongly agree

9. How would you rate your pain:

10. How would you rate how scared you were during the stitches:

[figure not shown]

Figure 2. Use of Immersive Virtual Reality for Laceration Repairs in the Pediatric Emergency
Department
Guardian Survey

1. **Patient Gender:**

Male
 Female
 Non-binary
 Self-identify
 Prefer not to say

2. What is the patient's age? _____

3. Please indicate if the patient has a developmental disability:

A. The patient does not have a developmental disability
B. Autism
C. Cerebral Palsy
D. Intellectual disability
E. Speech delay
F. _____

4. Has the patient had stitches previously? _____

Yes
 No
 Unsure

5. Has the patient ever used Virtual Reality (VR) goggles before today? _____

Yes
 No
 Unsure

6. Did the patient use VR goggles for the procedure today? _____

Yes
 No

7. If, yes, would you use VR goggles again for this procedure? _____

Yes
 No
 Did not use today

8. During the procedure did the patient experience any symptoms (select all that apply)?

Did not experience any symptoms
 Dizziness
 Headache
 Nausea
 Vomiting
 Other (*describe below*)

9. How do you think the procedure went overall?

- Not well at all
- Somewhat not well
- Neutral
- Somewhat well
- Very well

10. In your opinion, did the virtual reality goggles make the procedure seem less scary to the patient?

[figure not shown]
- Strongly disagree
- Disagree
- Neutral
- Agree
- Strongly agree

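### No pain or fear score is taken before the repair, so the model cannot adjust for starting level; adding one is a cheap gain in precision whose size depends on a correlation the plan does not give

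*Combined protocol and SAP*

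**What the plan says.** Section 2.0 sets the aim ("The objective of this study is to determine if VR goggles can decrease patient pain and anxiety during simple laceration repairs") and the outcomes: "The primary outcome will be pain scores as assessed by the validated Wong Baker Faces Scale and anxiety scores", the latter on the Children's Fear Scale.

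Section 3.0 fixes the timing: "Following the laceration repair, the patient, guardian and health care provider will be surveyed". The patient form (Figure 1) has one pain item with no time anchor and one retrospective fear item: "How would you rate how scared you were during the stitches". The guardian and provider forms (Figures 2 and 3) also ask pain and fear once each. No score before the repair is described anywhere.

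Section 4.0 gives the analysis: "Generalized Linear Model (GLM) will be used to assess the effect of intervention on the outcomes of the surveys". No covariates are listed. Section 3.0 divides patients into ages 6-11 and 12-17, but section 4.0 does not say that this grouping enters the model.

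The size in section 3.0 is "240 patients randomized into two groups, 120 per group", with no power, effect size or standard deviation.

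**The concern.** Children reach the repair with different levels of pain and fear, and section 1.0 itself says that anxiety amplifies pain. Whatever part of the post-repair score is predictable from the starting level stays in the residual variance when no starting level is recorded. The treatment effect is then estimated with a wider interval than necessary.

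Two things are at stake. The first is precision: with no stated power, the plan cannot show that 120 per arm has any to spare. The second is description: if the arms differ by chance in starting fear or pain, nobody will be able to see it or allow for it.

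**Working it through.** **Inputs from the documents.** 120 patients per arm (section 3.0); "All statistical tests will be 2-sided" at p < 0.05 (section 4.0).

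**Inputs not in the documents, so assumed.** The correlation r between baseline and post-repair score, taken over 0.2 to 0.6. An effect of 0.30 SD, for illustration only. The child's own rating as the primary score, since section 2.0 does not say which of the three raters supplies it.

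**The plan's own figure.** The 120 per arm cannot be reproduced, because power, effect size and SD are absent. Working backwards, the effect detectable with 80% power is

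(1.960 + 0.842) × √(2/120) = 2.802 × 0.129 = 0.362 SD.

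This describes what 120 per arm can detect; it is not a target that the plan set.

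**Effect of baseline adjustment.** In a linear model with the baseline score as covariate, the residual variance is (1−r²) times the unadjusted variance. Hence

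- effective n per arm = 120/(1−r²)
- detectable effect = 0.362 × √(1−r²).

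For comparison, analysing change from baseline gives an effective n of 120/[2(1−r)].

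| r (assumed) | 1/(1−r²) | Effective n per arm, covariate | Detectable effect, 80% power (SD) | Power at 0.30 SD | Effective n per arm, change score |
|---|---|---|---|---|---|
| no baseline | 1.00 | 120 | 0.362 | 64.2% | – |
| 0.2 | 1.04 | 125 | 0.354 | 66.0% | 75 |
| 0.3 | 1.10 | 132 | 0.345 | 68.3% | 86 |
| 0.5 | 1.33 | 160 | 0.313 | 76.5% | 120 |
| 0.6 | 1.56 | 188 | 0.289 | 82.8% | 150 |

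The covariate never does worse than ignoring the baseline, apart from one degree of freedom. The change score loses precision below r = 0.5 and gains nothing at 0.5. The form of the adjustment therefore has to be written down.

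**Chance imbalance.** The difference between arms in mean baseline score has standard error √(2/120) = 0.129 SD. A gap of 0.2 SD or more in either direction corresponds to z = 0.2/0.129 = 1.55, which arises in about 12% of trials. At r = 0.5 such a gap moves the unadjusted estimate by 0.5 × 0.2 = 0.10 SD.

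**The case against.** The strongest reply is that nothing here is wrong. Randomisation protects the comparison without any baseline, and measuring once afterwards is a legitimate choice for an unfunded pragmatic study in an emergency department. That stands, and it is why this is a recommendation.

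Several limits on the gain also stand.

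- **Pain.** A score before allocation reflects the wound; the outcome concerns the repair, after local analgesia. The documents do not say whether topical analgesia is applied before consent. The correlation for pain may therefore be lower than for fear, and one value of r should not be assumed for both.
- **Matching of items.** A question about the present moment does not correspond exactly to a retrospective fear item or to a pain item with no time anchor, which may lower r further.
- **Later care.** Midazolam, holding and Child Life support vary between children by design. A baseline score does not capture variation from care given afterwards.
- **Model.** The formula is for a linear model. The scales are short and ordered, and section 4.0 does not name the GLM family, so the exact factors need not carry over.
- **Covariates already collected.** Section 4.0 names none but excludes none. Age, previous stitches and previous VR use are on the forms and could be used.
- **Reactivity.** Asking about fear just before stitching might change it slightly. Because the question precedes allocation, any such effect falls on both arms alike.

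A reader might infer that the missing baseline costs the trial a third of its effective size. The documents do not support that: the figure needs r = 0.5, and no correlation is given. A reader might also infer that the comparison is biased, or that a baseline would cure reporting bias from raters who know the allocation. Neither follows.

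**Conclusion.** The point holds as an improvement to the design. Both primary scores are taken only after the repair and no covariates are specified, so the planned comparison is valid but less precise than it could be, and balance in starting pain and fear cannot be examined.

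The gain is between about 4% and 56% more effective patients per arm for r between 0.2 and 0.6, probably towards the lower part of that range for pain. It rests on an assumed r, a linear model and the child's own rating as outcome. The balance check has value even if r is small. This should be done if it is still practicable, but the trial can be interpreted without it.

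**What to change.** 1. After consent (and assent where it applies) and before the envelope is opened, have the child mark the Wong-Baker faces and the Children's Fear Scale once, for how they feel right now.
2. On the same sheet, record whether topical analgesia has already been applied.
3. Add to section 4.0: *The GLM for each primary score includes treatment arm, the baseline value of that score as a covariate (change scores will not be analysed), and age group (6-11, 12-17).* Name the GLM family in the same place.
4. Report both baseline scores by arm.

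**Cost.** Two face items on paper, perhaps a minute per child (an assumption), a small form change and one sentence in the analysis section. A research team member is already in the room to obtain consent. The age-group term needs no new data. If enrolment has begun, children already enrolled will have no baseline score, and the analysis section should say how they are kept in the model.

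### Pain and fear are both primary, but the plan names no rater, success rule or adjustment; if either scale on one rater can support a claim, the false-positive rate is about 7–10% instead of 5%

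*Combined protocol and SAP*

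**What the plan says.** Section 2.0 puts two instruments under one primary outcome: "The primary outcome will be pain scores as assessed by the validated Wong Baker Faces Scale and anxiety scores", the latter measured with the Children's Fear Scale. Section 1.0 gives the aim as finding out whether the goggles "improve patient pain and anxiety scores during simple laceration repair".

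Section 3.0 says that after the repair "the patient, guardian and health care provider will be surveyed". All three forms carry both scales: items 9 and 10 of the patient survey (Figure 1), items 11 and 12 of the guardian survey (Figure 2) and items 9 and 10 of the provider survey (Figure 3). On help with the child's form, Section 3.0 says: "The parent should complete the survey first before the child should the child need assistance with completion".

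Section 4.0 is the whole analysis plan. On the treatment comparison: "Generalized Linear Model (GLM) will be used to assess the effect of intervention on the outcomes of the surveys". On the three raters together: "The correlation between provider's, parent's, patient's survey will be analyzed using the Spearman's correlation test". On significance: "All statistical tests will be 2-sided and $p < 0.05$ will be considered as statistically significant".

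**The concern.** Two scales and three raters give six scores that could each be called primary. Three decisions needed to define a positive trial are not written down:

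- **Rater.** The GLM sentence covers the surveys without ranking them. The Spearman analysis describes agreement between raters and does not choose one. If child, guardian and provider disagree, nothing says whose score decides.
- **Success rule.** Nothing says whether pain alone, fear alone, or only both together would count.
- **Error rate.** The 0.05 threshold applies to each test. There is no split, order, adjustment or overall error rate.

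As written, rater and rule could be settled after the results are seen. If either scale can then carry the claim, the primary conclusion has a higher false-positive rate than the 0.05 threshold suggests.

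**Working it through.** **Inputs from the plan.** Two primary scales (Section 2.0); two-sided 0.05 per test (Section 4.0); 120 patients per group (Section 3.0). The plan states no overall error rate, power, effect size or standard deviation, so it has no figure of its own to reproduce on this point.

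**Input assumed.** The correlation r between the pain and fear test statistics on one rater. The documents give none, so r runs from 0 to 0.9. Section 1.0 says "Medical procedures often elicit anxiety, which amplifies the pain response", which makes r = 0 the least likely case.

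**Step 1: false positives with no effect on either scale.** Z1 and Z2 are treated as bivariate normal with correlation r.

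- Either scale: 1 − P(|Z1| < 1.96 and |Z2| < 1.96). At r = 0 this is 1 − 0.95² = 0.0975.
- Either scale, favouring VR: 1 − P(Z1 < 1.96 and Z2 < 1.96). At r = 0 this is 1 − 0.975² = 0.0494. A single test gives 0.025.
- Both scales: 0.05 + 0.05 − P(either). At r = 0 this is 0.10 − 0.0975 = 0.0025.
- Holm: with no effect on either scale, an error needs at least one p below 0.025. At r = 0 this is 1 − 0.975² = 0.0494.

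| r | Either, two-sided | Either, favouring VR | Both required | Holm |
|---|---|---|---|---|
| 0 | 9.75% | 4.9% | 0.25% | 4.9% |
| 0.3 | 9.5% | 4.8% | 0.5% | 4.8% |
| 0.5 | 9.1% | 4.5% | 0.9% | 4.7% |
| 0.7 | 8.4% | 4.2% | 1.7% | 4.3% |
| 0.8 | 7.8% | 3.9% | 2.2% | 4.0% |
| 0.9 | 7.0% | 3.5% | 3.0% | 3.6% |

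If one scale truly responds and the other does not, the both-required rule errs at most 5% of the time, because the unaffected scale must still reach p < 0.05.

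**Step 2: power at 120 per arm**, using a normal approximation to the GLM.

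- Effect detectable with 80% power on one scale at 0.05: (1.960 + 0.842) × √(2/120) = 0.36 SD. At 0.025: (2.241 + 0.842) × √(2/120) = 0.40 SD.
- Holm, only one scale responding at 0.36 SD: P(Z > 2.241 − 2.802) = 71%, down from 80%.
- Holm, both responding at 0.36 SD, at least one success: at r = 0, 1 − (1 − 0.712)² = 92%; at r = 0.9, 77%.
- Holm, both responding, power per scale: half of P(at least one success) + P(both succeed). At r = 0, P(both succeed) = 0.80² − (0.80 − 0.712)² = 0.632, so power per scale is (0.917 + 0.632)/2 = 77%. At r = 0.9 it is 75%.
- Both required, each scale having 80% alone: at r = 0, 0.80² = 64%; at r = 0.9, 75%.

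**The case against.** **The outcome is singular and its parts are joined by a conjunction, so both scales are required.** That reading is fair, and under it there is no inflation. But the plan does not state it, and the Section 4.0 threshold would let either scale be called significant alone. Nor does the plan mention the power that a joint requirement costs.

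**The patient's pain and fear scores are naturally the child's own.** Section 1.0 does favour this, and the gap on rater is smaller for it. Still, the phrase says whose pain is meant, not who rates it. The guardian and provider forms also rate the patient's pain and fear, and the analysis section does not separate the three.

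**Pain and fear could be two separately labelled conclusions, each at 0.05.** Whether those need joint control is a matter of judgement. A sponsor may take that position, but the plan should then say so and give up any single overall claim of success.

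**A stronger reading a reader might infer** is that any of six scores decides. With six independent tests the false-positive rate would be 1 − 0.95⁶ = 26.5%. The documents do not support this figure. No section says that any of the six scores is enough, and ratings of one child by three observers will hardly be independent. With an assumed common correlation of 0.9 the figure is about 11%. The open choice of rater adds to the one-rater error, but the documents do not allow the amount to be fixed.

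**Conclusion.** The point holds in a conditional form. What is certain is that the plan does not define a positive primary result: rater, success rule and error control are all unstated. The size depends on the rule. If either scale on one rater can support a claim, the two-sided false-positive rate is about 7–10%, and 3.5–4.9% favouring VR against 2.5% for one test. This assumes correlations of 0.9 down to 0. If both scales are required on one named rater, there is no inflation. A reader should therefore not conclude that the trial as planned has a 10% error rate, only that the text does not rule this out. The gap should be fixed before the data are examined and needs no redesign.

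**What to change.** In Sections 2.0 and 4.0, before data are examined:

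1. Name the child's self-reported Wong-Baker score and self-reported Children's Fear Scale score as the two primary endpoints. The essential step is to name one rater; the child fits the stated aim best.
2. Test them with Holm's procedure at an overall two-sided 0.05: the smaller p-value against 0.025 and, if that succeeds, the other against 0.05. Either scale can then support its own claim. If the sponsor intends a joint claim on pain and anxiety, state instead that both must reach p < 0.05, without adjustment.
3. Report guardian and provider scores as supportive estimates with confidence intervals.
4. Parent help with the child's form may be recorded and described by arm. Assisted surveys should stay in the analysis: help arises after randomisation and may differ by arm, so dropping them could bias the comparison.

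**Cost.** Wording, plus some power at 120 per arm. Under Holm, if only one scale responds at 0.36 SD, its power falls from 80% to about 71%. If both respond at 0.36 SD, power per scale is about 75–77% and the chance of at least one success is about 77–92% (correlation 0.9 to 0). Under the both-required rule, power is about 64–75% when each scale alone has 80%; returning to 80% at the same effect would take about 135–158 per arm (correlation 0.9 to 0). If that rule is chosen, the plan should state the loss.
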